12.5. Statistical plan

The activity of the test product at each study time will be expressed in absolute values versus baseline (T0).

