1. RATIONALE AND AIM OF THE STUDY

People lose collagen all over the body, not just in the face; skin roughness and laxity of the dorsum of the hands can result from chrono and photo-aging.

This skin roughness and laxity can range from very mild to severe; injection procedures can provide new tone and firmness to the skin of the hand dorsum.

Dermal fillers are the most used non-permanent injectable materials available today to correct skin flaccidity and roughness on the dorsum of the hands. They give immediate aesthetic effect due to elastic gel matrix injected and impart longer term effects due to bio stimulation, promoting new collagen formation.

The objective of this study is to investigate the aesthetic performance of the Hyaluronic acid (HA)-based dermal filler Prohilo® Body injected by a blunt tip microcannula (25G or 22G, preferably 22G), with fanning technique through a single entry point performing 5 passages and injecting 0,3 ml per passage, 1,5 ml for each hand. Volunteers of both sexes, aged 18-65 years with mild-moderate skin roughness and laxity at the level of hand dorsum are to be treated.

Primary endpoint of the study is the evaluation of performance and tolerance of Prohilo Body (3ml) treatment in the back of the hands (or dorsum of the hands).

Secondary endpoint is self-assessment questionnaire by both doctors and volunteers.

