4. DESIGN OF THE STUDY

Open, monocentric.

3 visits, 55 subjects.

T0: inclusion/exclusion criteria**, instrumental and clinical evaluation*, 1° treatment

T1 (after 1 month): instrumental and clinical evaluation, 2° treatment

[figure not shown]
T2 (3 months after T1; 4 months after T0): instrumental and clinical evaluation, NO treatment

Visit number	Study Activities	Treatment
1 T0	
Information and consent form provided. If participants agreeable, to sign consent form.
 
Photographic assessment: - Clinical photography
 
Clinical assessment
 
Instrumental assessment
 
First treatment of Profhilo® (refer to study protocol)
	
Prophilo Body 3 ml 1.5 ml per hand injected by a blunt tip microcannula (25G or 22G, preferably 22G), with fanning technique through a single entry point performing 5 passages and injecting 0,3 ml per passage.

2 T1 (1 month after T0)	
Photographic assessment: - Clinical photography
 
Clinical assessment
 
Instrumental assessment
 
Second treatment of Profhilo® (refer to study protocol)
 
Self-evaluation questionnaire
	
Prophilo Body 3 ml 1.5 ml per hand injected by a blunt tip microcannula (25G or 22G, preferably 22G), with fanning technique through a single entry point performing 5 passages and injecting 0,3 ml per passage.

3 T2 (4 months after T0)	
Photographic assessment: - Clinical photography
 
Clinical assessment
 
Instrumental assessment
 
NO treatment
 
Self-evaluation questionnaire
	No

DERMING S.r.l., Clinical Research and Bioengineering Institute [name]

[figure not shown]
[contact] - www.derming.com

Test code: E0122

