5.2. Number of volunteers

In order to obtain at least 50 evaluable cases, 55 volunteers will be enrolled in the trial

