6. CASE RECORD FORM (CRF)

The investigator will use an electronic CRF (eCRF) specially “ad hoc” engineered for each study by a trained and specialized DERMING technician. In the eCRF all information about subjects (personal data, subject’s history, inclusion/exclusion criteria, clinical evaluations, instrumental data etc.) will be recorded directly on a tablet (interactive form). The tabulation of the collected data is direct and totally automatic (not manual), assuring an higher level of quality and security. Every step of the eCRF creation and filling processes are performed in accordance to DERMING internal quality procedure assuring the validation of data and the prevention of data loss.

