8.2. Efficacy evaluation

The assessment of the aesthetic result will be established through the use of qualitative (clinical evaluations) and quantitative assessments (instrumental measurements) and supported by photographic documentation.

All clinical and instrumental evaluations will be carried out mono-laterally on hands, right or left side according to a subjects’ randomization list defined by the investigator before the subjects’ inclusion. The evaluation side assigned at each enrolled subject will be recorded in the eCRF.

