8.2.1. Clinical evaluations

Clinical assessment of hand dorsum (according to a reference photographic scale) roughness and laxity will be performed at each study time according to a visual score from 1 (no roughness and flaccidity) to 5 (very severe roughness and flaccidity).

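### The performance half of the primary endpoint is tied to no variable, visit, alpha or decision rule, so a favourable result on any one of at least 16 comparisons with T0 could be presented as showing performance.

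*Combined protocol and SAP*

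**What the plan says.** - **Primary endpoint (section 1):** "Primary endpoint of the study is the evaluation of performance and tolerance of Prohilo Body (3ml) treatment in the back of the hands". No measure, visit or threshold is attached to performance.
- **Secondary endpoint (section 1):** "Secondary endpoint is self-assessment questionnaire by both doctors and volunteers". No clinical or instrumental measure is therefore ranked below the primary.
- **Efficacy (section 8.2):** "The assessment of the aesthetic result will be established through the use of qualitative (clinical evaluations) and quantitative assessments (instrumental measurements"), supported by photographs. Sections 8.2.1 to 8.2.3.3 then list the measures without ranking them. The clinical measure is a "visual score from 1 (no roughness and flaccidity) to 5 (very severe roughness and flaccidity").
- **Visits (section 4):** clinical and instrumental assessments are made at T0, at T1 (one month, listed before the second treatment) and at the last visit: "T2 (3 months after T1; 4 months after T0): instrumental and clinical evaluation, NO treatment".
- **Analysis (section 12):** 12.1 gives means, standard deviations and graphs at the protocol times. 12.3 gives an unnamed non-parametric test for clinical data. 12.4 chooses between parametric and non-parametric tests by Shapiro-Wilk. 12.5 reads: "The activity of the test product at each study time will be expressed in absolute values versus baseline (T0"). The only 5% in the section is the normality threshold in 12.4.
- **Sample size (section 5.2):** "In order to obtain at least 50 evaluable cases, 55 volunteers will be enrolled in the trial". No effect size, power or alpha is given from which an intended primary variable could be inferred.

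**The concern.** A primary endpoint should have a yes-or-no answer fixed before the data are seen. Here the question of whether the product performed has no defined answer. A reader of the final report could not tell whether the highlighted variable and visit were chosen in advance or because they came out well.

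The open choice of visit also matters in substance. T1 follows one treatment and T2 follows two, so it is not settled which treatment course a performance statement would describe. For the torsion and profilometry parameters the plan does not say which direction of change is favourable, so either direction could be called a benefit.

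The study has no control arm, so pre-specification is one of the few protections against a chance finding.

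**Working it through.** **The plan's own figure.** Section 5.2 enrols 55 to obtain 50 evaluable, an implied loss of 5/55 = 9.1%. The 50 itself cannot be reproduced, because no alpha, power, effect size or SD is stated. The sample size therefore gives no clue to a primary variable.

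**Count of comparisons.**

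| Source | Variables |
|---|---|
| 8.2.1 clinical score | 1 (2 if roughness and laxity are separate; the text is unclear) |
| 8.2.3.1 dielectric constant, 0.5 and 1.5 mm probes | 2 |
| 8.2.3.2 profilometry, parameters plural and unnamed | at least 1 |
| 8.2.3.3 torsion: Ue, Uf, Uv, Ur | 4 |
| Total | at least 8 (or 9) |

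Two post-baseline visits against T0 give 8 x 2 = 16 comparisons at least, or 9 x 2 = 18. The questionnaire (secondary) and the photographs (no score defined) are left out.

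**Assumptions for the illustration (none is in the documents).** Two-sided 5% per test, a separate test per variable and visit, no true change, and any one improvement counted as success. Each test then has a 2.5% chance of a false improvement.

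**Chance of at least one false improvement.**
- Independent: 1 - 0.975^16 = 33.3%; 1 - 0.975^18 = 36.6%.
- One common correlation rho: 1 minus the integral over u of phi(u) x Phi((1.96 - sqrt(rho) u)/sqrt(1 - rho))^m, where m is the number of tests.

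| rho | 16 tests | 18 tests |
|---|---|---|
| 0.5 | 19% | 20% |
| 0.7 | 13% | 14% |
| 0.8 | 10% | 11% |
| 0.9 | 7% | 8% |

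- Structured simulation: correlation 0.8 or 0.9 within an instrument and 0.1, 0.3 or 0.5 between instruments, multiplied by 0.5 or 0.8 across visits. The result is 15-23% with 16 tests and 16-25% with 18. This fits the measures best, because four parameters come from one torque device and two from one dielectric device.
- One overall test per variable instead of one per visit: 8 tests give 18% if independent and 6% at rho 0.9; 9 tests give 20% and 6%.

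The ratio to 2.5% for one pre-specified test runs from 6.0/2.5 = 2.4 (8 tests, rho 0.9) to 36.6/2.5 = 14.6 (18 independent tests). For the structured case it is about 6 to 10.

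**If direction is left open.** The clinical score has a stated direction, and 8.2.3.1 says the dielectric constant rises with water content. Only torsion and profilometry lack a direction: 5 variables x 2 visits = 10 comparisons. Those 10 then have a 5% chance each, and the other 6 (or 8) have 2.5%:
- Independent: 1 - 0.975^6 x 0.95^10 = 48.6%; 1 - 0.975^8 x 0.95^10 = 51.1%.
- rho 0.9: 13.7% and 13.9%.

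The ranges are about 14-49% (16 tests) and 14-51% (18 tests).

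**The case against.** **The study is descriptive.** The stated aim is to investigate performance in an open, single-arm study, and 12.1 and 12.5 speak of means, graphs and values against baseline. Nothing mentions an endpoint being met. This has weight, and an openly exploratory label is an acceptable remedy. But the protocol does not call itself exploratory: it declares a primary endpoint and plans tests in 12.3 and 12.4.

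**Section 8.2 describes a joint assessment.** It does, and a reader should not treat success on any single parameter as the protocol's rule. It is not a decision rule either: nothing says how many measures must improve, or which prevail if they disagree.

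**T2 is obviously the primary visit.** It is the natural choice, but 12.5 covers every study time.

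**The error rates are assumed.** They are. Independence is implausible for parameters from one instrument, so 33-37% is an upper bound and the structured range should lead.

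Three stronger readings are tempting and are not supported:
- One favourable comparison would meet the primary endpoint. It could support performance only; tolerance is a separate part.
- Either-direction success applies to every comparison, giving 1 - 0.95^16 = 56% or 1 - 0.95^18 = 60%. Direction is open for only 10 comparisons.
- The sponsor intends to choose after seeing the data. The documents show only that the plan would allow it.

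**Conclusion.** The point stands and should be fixed before any data are analysed. In the text available, no variable, visit, efficacy alpha, decision rule or multiplicity rule is tied to performance, and section 12 runs unbroken from 12.1 to 12.5. This is established from the documents, as is the minimum of 16 comparisons.

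The size is illustrative and depends on the assumed 5% level, the correlations and the any-one-improvement reading. The most reasonable figure is a 15-25% chance of a false improvement, against 2.5% for one pre-specified test. Even the mildest case considered, 8 overall tests at correlation 0.9, gives 6%.

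**What to change.** **Change to sections 1 and 12.5, before any data are analysed:**
1. Name one primary performance variable, its favourable direction, T2 as the visit (after both treatments), and one named test at two-sided 5%. State that performance is shown only if that test is met.
2. One example is the change in clinical score from T0 to T2 by Wilcoxon signed-rank, which fits 12.3. It first requires stating whether roughness and laxity are one score or two, and which photographic scale applies to the hand dorsum, since section 15 lists only an inner arm scale. A named instrumental parameter is an alternative.
3. List the other clinical and instrumental parameters as secondary, naming the profilometry parameter and each favourable direction. Test them at T2 with Holm's correction only if the primary test is met. Otherwise, and at T1, report estimates with confidence intervals and make no claim.

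**Alternative, if no confirmatory claim is intended:** label all performance analyses exploratory, and report estimates with intervals and no statement that performance was shown.

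**Cost.** An amendment of which the Ethics Committee is informed (13.1), and possibly a change to the study-specific form: "The investigator will use an electronic CRF (eCRF"). No visit, measurement or subject is added, and the primary test keeps its full 5%.

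Power falls for any given secondary parameter. Take a paired t-test with n = 50, at the strictest Holm step with 7 parameters (0.05/7 = 0.0071) and given that the primary test is met. Power is then at least 76% instead of 93% for an assumed 0.5 SD change, and at least 51% instead of 79% for 0.4 SD.

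The change limits chance findings only. It does not make an uncontrolled before-after change attributable to the product.

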13. ETHIC

13.1. Ethic Committee approval

A final version of the study protocol and appendices will be submitted to an independent Ethic Committee (E.C.) to be examined. Moreover a copy of the E.C. approval has to be enclosed to the study documentation, while the Informed Consent Form has to be stored separately in order to respect the volunteers' privacy. No subject can be included in the trial before the Ethic Committee study approval. Moreover no volunteer can sign the Informed Consent Form before protocol inclusion.

Finally the Investigator agree to inform the Ethic Committee in case of protocol amendments and of serious or unexpected adverse events which could damage volunteers' safety or the study continuation. This study will be conducted according to the ethic of the "Helsinki Declaration" (see Appendix 7). A list of the members of the E.C., who examined the protocol, has to be enclosed in the Investigator's file.

The approval documentation has to enclose these information:

* the protocol title, the issue date, the Company and the Investigator's name.

* an approval declaration for the protocol and the CRF, with the annotations of each possible change.

* a list of E.C members

* the E.C President signature

* E.C. address (c/o DERMING S.r.l., Clinical Research and Bioengineering Institute, [name]).

The study will start only after Indipendent Ethical Committee approval.

DERMING S.r.l., Clinical Research and Bioengineering Institute [name]

[contact] - www.derming.com

Test code: E0122

13.2. Consent form for the volunteer

Each volunteer is precisely informed about the study and the personal data processing according to the European General Data Protection Regulation (GDPR 2016/679 see Appendix 6); before the inclusion each subject reads the information form related to the study and its methodology (see Appendices 3). Once informed the volunteer will complete and sign the consent form. At the end of the study the investigator will declare to have informed all the volunteers who participated in the protocol, signing and dating the relative form (see Appendix 4).

13.3. Product conformity to the current regulations

The test starts only after the evaluation of the documentation provided by the Investigator (with products identification, date and IBSA representatives' signature for knowledge).

This documentation contains:

- the declaration that the products are submitted to the E.C.C. legislation,
- the qualitative composition of the products with the declaration that no component presents a serious toxicological effects at the established concentration,
- all available data about toxicological and tolerability pre-clinical tests,
- the normal conditions of the products use,
- a Company attestation of insurance/statement of responsibility related to the risks for the volunteers who will use the products according to the foresee conditions of use.

The administration of the products can be stopped immediately as soon as the Investigator judges it necessary.

13.4. Insurance

The study is covered by the insurance policy n. of the insurance company for damages related to the study product and by insurance policies n. 0260/03/0024707 and 0260/03/0024695 of Reale Mutua insurance company for damages induced by the micro-injection procedure.

14. CONFIDENTIALITY

14.1. Final report

The final report contains: the identification of the tested product, a summary of the procedure, results' evaluation and conclusions about the clinical test.

15. APPENDICES

- 1) Product information and complications of injectable fillers
- 2) Adverse event and concomitant medication forms
- 3) Informed consent form and subjects' enrolment form
- 4) Certificate of subjects information
- 5) Volunteers' self assessment questionnaire
- 6) Consent form to the personal data processing (European General Data Protection Regulation - GDPR 2016/679)
- 7) Helsinki declaration
- 8) Inner arm reference photographic scale
- 9) "Torque on" and "torque off" curves.

